## **2.1 Aim 1. Identification of target population and high volume centers**

The prevalence of specific CRE is extremely variable in various patient populations. In addition, over time, prevalence patterns for specific CRE tend to change. The data collection carried out under this protocol will provide real-time data on which patients who are the target population for any trial directed against CRE infection. Also, the data collected will indicate which geographic areas and which centers have the highest incidence of CRE infections. This will facilitate rational site selection for future trials.

## **2.2 Aim 2. Provide data on impact of potential inclusion/exclusion criteria on enrollment in future trials**

Detailed clinical data will be collected to guide the future development of clinical trials. The eCRF is designed to collect data on the most common barriers to enrollment in clinical trials. Data can then be used in the design of future trials to be presented to pharmaceutical companies, as well as to regulators from the FDA, to provide a rationale for requesting exceptions in inclusion/exclusion criteria. This will result in clinical trials that are more readily generalizable (see 3.2 in main MDRO protocol).

## **2.3 Aim 3. Provide data on expected outcomes of patients with CRE infections for power and sample size calculations for future trials**

Detailed outcomes data will be collected. Data will include survival and microbiologic clearance outcomes when available. In addition, anatomical site specific clinical symptomatic outcomes, modeled on FDA guidance documents, will be documented. Data obtained will aid in guiding the design of future clinical trials by providing data needed for power and sample size calculations (see 3.3 in main MDRO protocol).

## **3 Laboratory Assessments**

As novel antibiotics directed against CRE may have differential efficacy based on the mechanism of resistance, molecular characterization for strain type and mechanism of carbapenem resistance will be performed on CRE isolates, including whole genome sequencing, single gene PCR, multilocus sequence typing (MLST) and/or rep-PCR (6). Furthermore, phenotypic characteristics such as *in vitro* susceptibility testing will be performed in the central research laboratories.

## **4 Exploratory Aims**

### **4.1 Exploratory Aim 1. The association between bacterial characteristics and clinical outcomes in patients with CRE**

### **4.2 Exploratory Aim 2. The association between treatment modalities and clinical outcomes in patients with CRE**

### **4.3 Exploratory Aim 3. Risk factors for baseline and treatment-emergent resistance to anti-CRE antibacterials in patients with CRE**

## 5 Study Population

All patients who are admitted to one of the participating hospitals and who have a CRE isolated from bloodstream infection source in a clinical culture will be included.

In addition, all participating hospitals in China will also enroll patients who meet the below criteria:

- a. have a CRE isolated from respiratory source in a clinical culture
- b. AND have a clinical diagnosis of pneumonia, per diagnosis criteria in Table 1

**Table 1.**

At least one criterion from each section must be present to meet definition of pneumonia diagnosis		
1	Radiographic Criteria	
 
• Chest radiograph showing the presence of new or progressive infiltrate(s) suggestive of bacterial pneumonia within 48 hours of all other diagnostic criteria being present
 

2	Respiratory Signs/Symptoms	
 
• New onset or worsening: cough, dyspnea, tachypnea (respiratory rate <math>\geq 25</math> breaths per minute for patients <math>>18</math> years, <math>>60</math> breaths per minute for children <math><1</math> year, <math>>40</math> breaths per minute for children ages 1-3 years, <math>>30</math> breaths per minute for children ages 4-12 years, <math>>20</math> breaths per minute for children 12-18 years), or expectorated sputum production
 
• Hypoxemia, defined as any of the following:               
 
▪ A partial pressure of oxygen <math><60</math> millimeters of mercury measured by arterial blood gas (ABG)
 
▪ A worsening (decrease <math>>10\%</math>) of the ratio of arterial partial pressure of oxygen to fraction of inspired oxygen (<math>\text{PaO}_2/\text{FiO}_2</math>)
 
▪ Pulse oximetry reading of <math><90\%</math>
 
▪ New supplemental oxygen requirement
 
▪ Greater than 2LPM increase in amount of supplemental oxygen required for patients on chronic supplemental oxygen therapy
 
▪ Need for acute changes, after 2 days stability, in ventilator support system to enhance oxygenation, as determined by worsening oxygenation (ABG or <math>\text{PaO}_2/\text{FiO}_2</math>) or needed changes in the amount of positive end-expiratory pressure
 
 
 

3	Systemic Inflammation	
 
• Documented body temperature <math>\geq 38</math> degrees Celsius or <math>\leq 35</math> degrees Celsius (core body temperature)
 
• Leukocytosis, defined as total peripheral white blood cell count <math>\geq 10,000</math> cells/cubic millimeter
 
• Leukopenia, defined as total peripheral white blood cell count <math>\leq 4,500</math> cells/cubic millimeter
 
• Greater than 15% immature neutrophils (bands) noted on peripheral blood film
 

## 6 Clinical Definitions

**CRE:** For the purposes of this study, CRE are defined as any Enterobacteriaceae displaying in vitro resistance to any of the carbapenems as per CDC guidelines, i.e. Enterobacteriaceae that are resistant to any carbapenem antimicrobial (i.e., minimum inhibitory concentrations of  $\geq 4$  mcg/ml for doripenem, meropenem, or imipenem OR  $\geq 2$

mcg/ml for ertapenem) OR Documented to produce carbapenemase.

In addition:

- For bacteria that have intrinsic imipenem nonsusceptibility (i.e., *Morganella morganii*, *Proteus* spp., *Providencia* spp.), resistance to carbapenems other than imipenem is required.

## **7 Statistical Analysis Plan**

### **7.1 Sample Size Estimate**

The sample size is estimated to be between 3,000-5,000 unique admissions.

## Appendix II:

SNAP: Study Network of *Acinetobacter baumannii* as Carbapenem-Resistant Pathogen

### List of Abbreviations

SNAP	Study Network of Acinetobacter baumannii as Carbapenem-Resistant Pathogen
CRAb	Carbapenem-resistant Acinetobacter baumannii
PCR	Polymerase Chain Reaction
rep-PCR	Repetitive extragenic palindromic polymerase chain reaction

## 1 Background

*Acinetobacter baumannii* has emerged as one of the most highly antimicrobial-resistant pathogens causing hospital-acquired infections globally. In the U.S., an estimated 45,000 cases of *A. baumannii* infections occur per year. The most common presentations of invasive infection include bacteremia and pneumonia. *A. baumannii* has an extraordinary ability to develop resistance to even the most potent antimicrobial agents. In particular, carbapenem resistance among *A. baumannii* has dramatically increased in the last decade, with rates increasing from 21% in 2003-2005 to 48% in 2009-2012. According to recent CDC data, 55% of *A. baumannii* causing ventilator-associated pneumonia in the U.S. are resistant to carbapenems. Treatment options for carbapenem-resistant *A. baumannii* (CRAb) infections are extremely limited and include agents such as colistin, tigecycline and minocycline, which have uncertain efficacy and considerable toxicity. Risk factors for acquiring CRAb include exposure to antimicrobial agents, presence of indwelling catheters, severity of illness, and length of hospital stay especially in intensive care units. In-hospital and 30-day all-cause mortality from CRAb infections are estimated to be 42%-62% and 16%-58%, respectively. Despite this significant disease burden, prospective multicenter studies that evaluate microbiological factors that impact patient outcome – while carefully controlling for clinical co-variables – have not yet been conducted in the U.S.

## 2 Objective

The objective of this study is to provide observational data that will aid in the design of randomized clinical trials on therapeutics and diagnostics for CRAb infections. To this end, clinical and epidemiological data will be collected on patients who have CRAb isolated from clinical cultures during hospitalization as well as descriptions of the outcomes of patients treated with various antimicrobial regimens. Molecular and

microbiological characterization will also be performed on CRAB isolates.

### **2.1 Aim 1. Identification of target population and high volume centers**

The prevalence of specific CRAB is extremely variable in various patient populations. In addition, over time, prevalence patterns for specific CRAB tend to change. The data collection carried out under this protocol will provide real-time data on which patients are the target population for any trial directed against CRAB infection. Also, the data collected will indicate which geographic areas and which centers have the highest incidence of CRAB infections. This will facilitate rational site selection for future trials.

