## Protocol Summary

Protocol Title:	Multi-Drug Resistant Organism Network - MDRO
Study Design:	Master protocol for prospective, multicenter, observational cohort studies
Study Population:	Hospitalized patients with multi-drug resistant organisms
Number of subjects:	To be specified in each study sub-protocol as outlined in Appendices
Clinical Samples:	Multi-drug resistant organism isolates from specimens obtained from any anatomic site
Estimated Start of Enrollment:	Second quarter of 2016
Estimated Time to Completion:	Second quarter of 2019

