## **4 Enrollment Target**

The study will enroll up to 2000 unique admissions. This will be a global competitive enrollment.

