## 7 Statistical Analysis Plan

### 7.1 Sample Size Estimate

The sample size will be approximately 2000 unique admissions.

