## 5.2 Outcome analyses

The difference in proportion in 30- and 90 day mortality will be summarized with confidence intervals. The IPW difference in proportion, with 95% CI, will also be summarized. Pairwise DOOR probabilities and 95% CI will be estimated using Halperin's method. Both an unadjusted and IPW adjusted DOOR probability with 95% CI will be estimated. IPW models for infection vs. non-infection comparisons included:

- Geographic region
- Immunocompromising conditions
- Preadmission location (home origin vs other)
- Age-adjusted Charlson comorbidity index

IPW models for regional comparisons (infections only) included:

- Anatomical source of infection
- Immunocompromising conditions
- Preadmission location (home origin vs other)
- Age-adjusted Charlson comorbidity index

Post hoc, a logistic regression model was used to explore risk factors for mortality. Variables included in the analysis were:

- Geographic region (USA as reference)
- Anatomical source of infection (blood as reference)
- Aged-adjusted Charlson comorbidity index
- Immunocompromising conditions
- Pre-admission location
- Monomicrobial vs polymicrobial culture
- Acquired carbapenemase gene
- Clonal group (CG2 as reference)
- Capsular polysaccharide locus (KL)
- Lipooligosaccharide outer core locus (OCL)
- Site (random effect)

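### Region is a planned comparison under competitive enrolment with no stated common window, yet no SAP listing, table or model carries calendar time, so regional contrasts could partly reflect enrolment period

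*Protocol*

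**What the plan says.** Protocol, Appendix II, section 2.1 (Aim 1) states: "In addition, over time, prevalence patterns for specific CRAB tend to change". Section 4 sets a ceiling of 2000 unique admissions and adds: "This will be a global competitive enrollment". Section 7.1 repeats the number: "The sample size will be approximately 2000 unique admissions". No regional quota or common start and stop date is given. The Protocol Summary plans network enrolment from "Second quarter of 2016" to completion in "Second quarter of 2019", about three years.

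In the SAP, section 2.2 lists geographic region among the a priori comparisons, for all subjects and for infections only. Section 2.3 expects patient characteristics, outcomes and strains to differ by region, and says this will inform trial design. Section 3.1 plans a global test across regions and pairwise comparisons against the USA, two-sided at 0.05. Section 5.2 introduces the weighting model with "IPW models for regional comparisons (infections only) included". It then names four covariates: anatomical source, immunocompromise, preadmission location and age-adjusted Charlson index.

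**The concern.** Regions that join at different times sample the organism at different times. If clones, carbapenemases or susceptibility shift over the enrolment years, a region that enrolled mostly early will look different from one that enrolled mostly late, even with no geographic difference. A timing gap could also hide a real difference. The SAP offers no way to see either case, because nothing in the report would show when each region's patients were cultured.

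What is at stake is the use of the regional contrasts in planning trials, which SAP 2.3 names as their purpose. The strain, carbapenemase and susceptibility tables have no adjustment of any kind. By weighting the regional outcome comparisons, the SAP already accepts that crude regional differences may be confounded.

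**Working it through.** **1. Is calendar time anywhere in the SAP?**

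| Place in SAP | What it contains | Calendar time? |
|---|---|---|
| 5, enrolment listings | By region; by region and site | No |
| 5, column variables | Region, infection status, carbapenemase, meropenem MIC, clonal group | No |
| 5.1, row variables | Time appears only as durations (admission to culture; culture or admission to discharge or death) | No |
| 5.2, regional IPW model | Source, immunocompromise, origin, Charlson | No |
| 5.2, post hoc logistic model | Region, source, Charlson, immunocompromise, origin, polymicrobial culture, carbapenemase, clonal group, KL, OCL, site as random effect | No |

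A random site effect does not remove a timing difference between regions. The variable can be derived: SAP 3.2 counts the 30-day DOOR from the date of culture collection.

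**2. Size of a possible artefact**

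The plan has no figure to reproduce. With no true regional effect and a linear drift common to both regions:

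false difference = drift per year × gap in mean enrolment date.

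The documents supply neither term. Purely to show scale, assume drift of 1 or 2 points a year, 400 patients per region and a base rate of 37%. That rate is the midpoint (16 + 58)/2 of the 30-day range in "In-hospital and 30-day all-cause mortality from CRAb infections are estimated to be 42%-62% and 16%-58%, respectively". The standard error of a difference is √(2 × 0.37 × 0.63/400) = 3.4 points.

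| Gap (years) | Drift 1: false difference; rejection at 5% | Drift 2: false difference; rejection at 5% |
|---|---|---|
| 0 | 0; 5% | 0; 5% |
| 0.5 | 0.5 points; 5% | 1 point; 6% |
| 1 | 1 point; 6% | 2 points; 9% |
| 2 | 2 points; 9% | 4 points; 21% |

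The last row is extreme. If two regions enrol for a and b years at opposite ends of a three-year period, the midpoint gap is 3 − (a + b)/2. A gap of 2 then needs a + b = 2, that is, windows averaging one year with no overlap. If all regions close together and accrue steadily, a start lag of L years gives a gap of only L/2, so lags of 1 to 2 years give gaps of 0.5 to 1.

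**3. Cost of adjusting for date**

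For uniform accrual in two equal groups, adjusting linearly for date multiplies the standard error by 1/√(1 − R²). Here R² = (gap²/4)/(gap²/4 + w²/12), and w is the window length.

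- Identical windows: gap 0, R² = 0, factor 1.
- Years 0–2 against 1–3: gap 1, w = 2, R² = 0.25/(0.25 + 0.333) = 0.43, factor 1.32.
- Years 0–1.5 against 1.5–3: gap 1.5, w = 1.5, R² = 0.5625/(0.5625 + 0.1875) = 0.75, factor 2.

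A simulation (1,000 runs, 400 per region) agrees: the standard deviation of the regional estimate rose from 3.45 to 4.55 points in the second case and from 3.45 to 6.75 in the third. In the third case the adjustment rests wholly on extrapolating a trend.

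**The case against.** The strongest reply is that no gap has been shown. Competitive enrolment permits unequal windows but does not prove them. A shared cap, if reached, closes all regions together, so they would differ mainly in start date. That stands, and it is why the point is worded as a possibility.

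Second, the Aim 1 sentence concerns prevalence patterns. It says nothing about mortality, DOOR or care. That also stands: the text bears on the strain, carbapenemase and susceptibility tables, and its extension to outcomes is an assumption.

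Third, the logistic model already includes carbapenemase, clonal group, KL and OCL, so it captures part of any strain-related drift. This is correct, but neither the regional IPW comparisons nor the tables have such terms.

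Fourth, the study is observational, and its primary objective, 30-day mortality of CRAB infections, is not altered by this point. That limits the weight of the point but does not remove it, since region is a tested comparison.

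A reader might go further and take a drift rate from Appendix II, section 1: "with rates increasing from 21% in 2003-2005 to 48% in 2009-2012". Between period midpoints that is (48 − 21)/(2010.5 − 2004) = 4.2 points a year, which would suggest false regional differences of 4 to 8 points for gaps of 1 to 2 years. The documents do not support this. That figure is the carbapenem-resistant share of all *A. baumannii*. SNAP admits only carbapenem-resistant isolates (Appendix II, section 6), and SAP 2.5 also excludes those not meropenem-resistant centrally. The share is therefore fixed by design and cannot drift within this cohort.

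A reader might also infer that Aim 1 promises a trend analysis that the SAP fails to deliver. Aim 1 promises current data on the target population and on where incidence is highest. It does not commit to a table by year.

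**Conclusion.** The omission is real and can be verified from the text: region is an a priori comparison tested against the USA, enrolment has no stated common window, and calendar time is absent from every listing, table and model. Regional contrasts could therefore partly reflect enrolment period, most directly in the unadjusted strain, carbapenemase and susceptibility tables.

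The size cannot be stated from the documents. It is zero if regions enrolled over the same period. The figures under the working rest on assumed drift, gap, group size and base rate, and show scale only. It would be wrong to conclude that regional differences in mortality or DOOR are in fact differences in calendar time. This is a moderate, inexpensive improvement to a planning analysis and does not affect the primary objective.

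**What to change.** 1. In the SAP section 5 listings, tabulate year or half-year of index culture by region and by site. This alone shows whether there is a gap.
2. As a sensitivity analysis, add calendar period to the regional IPW model and to the post hoc logistic model in 5.2.
3. Repeat the regional comparisons, including the strain, carbapenemase and susceptibility tables, restricted to the window in which all compared regions were enrolling.
4. If windows barely overlap, do not rely on the adjustment. State that region and period cannot be separated.
5. Since SAP 2.2 separates a priori from post hoc analyses, list these as post hoc.

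A separate table of strain features and mortality by year is optional.

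The cost is one variable derived from a date already held, plus SAP wording. Intervals widen: not at all with identical windows, by about a third with the partial overlap shown above, and to about double with none. The shared-window analysis uses fewer patients.

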### **2.2 Aim 2. Provide data on impact of potential inclusion/exclusion criteria on enrollment in future trials**

Detailed clinical data will be collected to guide the future development of clinical trials. The eCRF is designed to collect data on the most common barriers to enrollment in clinical trials. Data can then be used in the design of future trials to be presented to pharmaceutical companies, as well as to regulators from the FDA, to provide a rationale for requesting exceptions in inclusion/exclusion criteria. This will result in clinical trials that are more readily generalizable (see 3.2 in main MDRO protocol).

### **2.3 Aim 3. Provide data on expected outcomes of patients with CRAB infections for power and sample size calculations for future trials**

Detailed outcomes data will be collected. Data will include survival and microbiologic clearance outcomes when available. In addition, anatomical site specific clinical symptomatic outcomes, modeled on FDA guidance documents, will be documented. Data obtained will aid in guiding the design of future clinical trials by providing data needed for power and sample size calculations (see 3.3 in main MDRO protocol).

## **3 Exploratory Aims:**

- To establish a prospective cohort of subjects with carbapenem-resistant *Acinetobacter baumannii* infection or colonization
- To describe the demographics, natural history and clinical outcome of patients with CRAB
- To collect the associated *A. baumannii* strains of patients with CRAB for future studies

## **4 Enrollment Target**

The study will enroll up to 2000 unique admissions. This will be a global competitive enrollment.

## **5 Study Population**

All patients who are admitted to one of the participating hospitals and who have a CRAB isolated in a clinical culture will be included.

## 6 Clinical Definitions

**CRAB:** *Acinetobacter baumannii* isolates that are resistant (minimum inhibitory concentrations of  $\geq 8$  mcg/ml ) to at least one of the following three carbapenems: doripenem, imipenem, meropenem.

## 7 Statistical Analysis Plan

### 7.1 Sample Size Estimate

The sample size will be approximately 2000 unique admissions.

## Appendix III:

### VENOUS II: Vancomycin-Resistant Enterococci Outcomes Study II

#### List of Abbreviations

VENOUS II	Vancomycin-Resistant Enterococci Outcomes Study II
VRE	Vancomycin-Resistant Enterococci
BSI	Blood Stream Infection

## 1 Background

Vancomycin-resistant enterococci (VRE) are one of the leading causes of health-care associated infections, causing approximately 20,000 infections and 1,300 deaths per year in the US alone (1). Moreover, VRE are a major cause of bloodstream infections (BSI) and preferentially affect patients who are severely ill and have an impaired immune system, such as cancer patients and subjects in the intensive care setting (2). Currently, there is only one FDA-approved drug to treat VRE (linezolid). However, linezolid has major limitations for the treatment of severe VRE infections and its use in patients that need prolonged therapy is discouraged due to an unfavorable toxicity profile. Although several new drugs have been approved for the management of other important drug-resistant gram-positives (e.g. methicillin-resistant *Staphylococcus aureus*), the majority of these new compounds lack bactericidal activity against VRE. The most common anti-VRE used drug is daptomycin (off-label), a lipopeptide antibiotic with *in vitro* bactericidal activity against these organisms (3). However, the emergence of resistance during daptomycin therapy is a serious concern and uncertainty in the best dose regimen to treat severe VRE infections remains (4). Thus, robust clinical data to determine the best treatment approaches for these multi-drug resistant organisms are urgently needed. Indeed, despite the significant burden of disease caused by VRE, prospective multicenter studies evaluating clinical and microbiological factors that impact patient outcomes have not yet been conducted in the U.S.

